Appendix 3 ADR formVersion 1 – May 15th, 2017

CONFIDENTIAL Card unique number: 0000 0000 0000 0

Enhanced safety surveillance of seasonal influenza (flu) vaccine

Study of possible adverse events following immunisation – this surveillance is designed to capture all adverse events following immunisation. Please report if you get any symptoms following your “flu jab” (influenza vaccination).

1. About you – this information is kept confidential and won't leave your practice

About you* we need contact details, please supply a full address so we can link this to your medical record:

First name _____ Surname _____
 Address _____
 Postcode _____ Telephone: _____ Email _____ @ _____
 Signed _____ Date _____ / _____ /2017

*This personal information is only being collected to link any side effects to your record

2. When you were vaccinated / When was the influenza vaccination given

What date were you vaccinated / was the vaccine given _____ / _____ /2017

Where were you vaccinated: At your GP surgery: Yes No If no, say where: _____

3. If you were not the person vaccinated

Information about the person* Male Female Date of Birth _____ / _____ / _____

First name _____ Surname _____

4. Please report any side-effects/conditions in the 7 days after your flu vaccine

Please look at the list of possible vaccine side-effects on the next page – if the person vaccinated has experienced any adverse events – please tick the relevant box and indicate the severity

Please also mark if the symptoms/possible side effects are still persisting

Please return the card in the envelope provided to your GP – please return by post or in person.

Thank you for your help

5. If you had no side effects in the 7 days after vaccination tick and return

I/the person vaccinated has NOT had any side effects or other symptoms following vaccination:

Please return the card in the envelope provided to your GP – please return by post or in person.

Thank you for your help

Formal study name:

Post-authorisation passive enhanced safety surveillance of seasonal influenza vaccines:

Pilot study in England

GSK study abbreviation:

EPI-FLU 046 VS UK

Collaborating Study Sponsors:

University of Surrey, Guildford UK

GlaxoSmithKline Biologicals

Contact:

[name]

Professor of Primary Care and Clinical Informatics

E-mail: PPD

Telephone: +PPD

PPD

Practice Liaison Officer

E-mail: PPD

Telephone: +PPD

Enhanced safety surveillance of seasonal influenza vaccine

Possible side effect or Condition in the 7 days after influenza vaccination	Start date of the symptom	Please tick as appropriate
Conjunctivitis – Sticky eyes	____/____/17	
Runny nose	____/____/17	
Blocked nose	____/____/17	
Epistaxis – Nose bleed	____/____/17	
Common cold	____/____/17	
Cough	____/____/17	
Sore throat	____/____/17	
Hoarse voice	____/____/17	
Wheezing	____/____/17	
Decreased appetite	____/____/17	
Nausea – feeling sick	____/____/17	
Vomiting – being sick	____/____/17	
Diarrhoea	____/____/17	
Fever (add temperature if measured)	____/____/17	
Allergic reaction (rash)	____/____/17	
Other allergic reactions	____/____/17	
Facial oedema (swelling)	____/____/17	
Local reaction to vaccine	____/____/17	
Rash	____/____/17	
Irritability	____/____/17	
Drowsiness	____/____/17	
Fatigue	____/____/17	
Tremor / shaking	____/____/17	
Seizure / fits	____/____/17	
Headache	____/____/17	
Muscle aches	____/____/17	
Joint pain	____/____/17	
Other		
1. _____	____/____/17	
2. _____	____/____/17	
3. _____	____/____/17	
Add below if more		

Appendix 7 Practice feedback sample***Feedback on possible adverse events following vaccination***

[figure not shown]
The European Medicines Agency (EMA), as part of the monitoring of the continuing safety of the influenza vaccination, has circulated a list of codes for possible adverse events that may be associated with vaccination.

Data from will be used to monitor these possible adverse events, via twice-weekly data extract.

It is of course essential for this work that the data is accurate and that these codes are used consistently throughout the flu season. We therefore attach a table showing how many times the codes on the EMA list have been recorded in 's patient records in the 7 days from XXXX-XX-XX to XXXX-XX-XX.

Please continue to use these codes for all patients, whether or not they have been recently vaccinated. **Use of these codes does not imply a causal link between the adverse event and vaccination – any association will emerge from the data analysis.** This analysis will only be valid if the codes are used consistently for all relevant cases, regardless of the patient's vaccination status. It is therefore essential that these codes are used for all appropriate cases, whether or not the patient has been recently vaccinated.

Thank you very much for your help with this project – your input is crucial for ensuring that the influenza vaccination continues to be both safe and protective for patients

Following graph provides a visualization of compared with 7 other adverse events monitoring practices

CONFIDENTIAL

207781 (EPI-FLU-055 VS UK)

Final Protocol

The following table provides the total counts of possible adverse events for the 2015-09-04 to 2015-09-21 for your practice.

Disease Name	EMA surveillance condition	ReadCode Type	
Respiratory/Miscellaneous	Conjunctivitis	Preferred Read Code (F4C0.)	5
		Other Read Codes	0
	Rhinorrhoea	Preferred Read Code (1C83.)	0
		Other Read Codes	0
	Nasal congestion	Preferred Read Code (H1y1z)	0
		Other Read Codes	3
	Epistaxis	Preferred Read Code (R047.)	3
		Other Read Codes	22
	Coryza	Preferred Read Code (H00..)	1
		Other Read Codes	0
Gastrointestinal	Cough	Preferred Read Code (171..)	24
		Other Read Codes	1
	Oropharyngeal pain	Preferred Read Code (1922.)	1
		Other Read Codes	0
	Oropharyngeal pain	Preferred Read Code (1CB3.)	0
		Other Read Codes	0
	Hoarseness	Preferred Read Code (1CA2.)	1
		Other Read Codes	2
	Wheezing	Preferred Read Code (1737.)	3
		Other Read Codes	20
Fever/pyrexia	Decreased appetite	Preferred Read Code (R0300)	0
		Other Read Codes	2
	Nausea	Preferred Read Code (198..)	3
		Other Read Codes	0
	Vomiting	Preferred Read Code (199..)	2
Sensitivity/anaphylaxis		Other Read Codes	0
	Diarrhoea	Preferred Read Code (19F..)	11
		Other Read Codes	0
	Fever	Preferred Read Code (165..)	9
		Other Read Codes	0
Rash	Mild fever (<38.5°C rectal) High fever (>39.5°C)	Preferred Read Code (2E3..)	2
		Other Read Codes	0
	Hypersensitivity reactions	Preferred Read Code (SN52.)	1
		Other Read Codes	0
	Anaphylactic reactions	Preferred Read Code (SN52.)	0
General non-specific symptoms		Other Read Codes	0
	Facial oedema	Preferred Read Code (16J5.)	0
		Other Read Codes	7
	Local erythema	Preferred Read Code (SP3y5)	0
		Other Read Codes	0
	Rash	Preferred Read Code (M130.)	0
		Other Read Codes	18
	Generalised rash	Preferred Read Code (2114..)	0
		Other Read Codes	0
	Local erythema	Preferred Read Code (SP3y5)	0
		Other Read Codes	0
	Irritability	Preferred Read Code (225A.)	0
		Other Read Codes	1
	Drowsiness	Preferred Read Code (1B67..)	0
		Other Read Codes	1
	Fatigue	Preferred Read Code (168..)	3
		Other Read Codes	0
	Malaise	Preferred Read Code (N037..)	0
		Other Read Codes	3

(Continued on next page..)

*The following table provides the total counts of possible adverse events for the 2015-09-04 to 2015-09-21 for your practice.
(Continues from previous page..)*

Disease Name	EMA surveillance condition	ReadCode Type	
Neurological	Peripheral tremor	Preferred Read Code (1B22.)	0
		Other Read Codes	0
	Guillain-Barre Syndrome (GBS)	Preferred Read Code (F3700)	0
		Other Read Codes	0
	Seizure/ Febrile convulsions	Preferred Read Code (1B64.)	0
		Other Read Codes	0
Musculoskeletal	Seizure/ Febrile convulsions	Preferred Read Code (1B6B.)	0
		Other Read Codes	0
	Headache	Preferred Read Code (1B1G.)	5
		Other Read Codes	0
Musculoskeletal	Muscle aches/ myalgia	Preferred Read Code (N2410)	5
		Other Read Codes	34
	Arthropathy	Preferred Read Code (N037.)	0
		Other Read Codes	0

Possible adverse event code list for your reference

Disease Name	EMA surveillance Condition	Description	Read Code
Respiratory/Miscellaneous	Conjunctivitis	Acute conjunctivitis	F4C0..
	Rhinorrhoea	Rhinorrhoea	1C83..
	Nasal congestion	Nasal airway obstruction	H1y1z
	Epistaxis	Epistaxis	R047..
	Coryza	Acute coryza	H00..
	Cough	Cough	171..
	Oropharyngeal pain	Sore mouth/Throat pain	1922..
	Oropharyngeal pain	Sore mouth/Throat pain	1CB3..
	Hoarseness	Hoarse	1CA2..
Gastrointestinal	Wheezing	Wheezing	1737..
	Decreased appetite	Loss of appetite	R0300
	Nausea	Nausea	198..
	Vomiting	Vomiting	199..
Fever/pyrexia	Diarrhoea	Diarrhoea	19F..
	Fever	Fever symptoms	165..
	Mild fever (<38.5° C rectal) High fever (>39.5°C)	O/E – Temperature level	2E3..
Sensitivity/anaphylaxis	Hypersensitivity reactions	Adverse drug reaction/Vaccine allergy	SN52..
	Anaphylactic reactions	Drug-induced anaphylaxis	SN501
	Facial oedema	Facial swelling	16J5..
	Local erythema	Erythema at injection site	SP3y5
Rash	Rash	Drug-induced rash	M130..
	Generalised rash	Rash	2I14..
	Local erythema	Erythema at injection site	SP3y5
General non-specific symptoms	Irritability	O/E - Irritable	225A..
	Drowsiness	Drowsiness	1B67..
	Fatigue	Fatigue	168..
Neurological	Peripheral tremor	Tremor	1B22..
	Guillain-Barre Syndrome (GBS)	Guillain-Barre Syndrome	F3700
	Seizure/ Febrile convulsions	Convulsion/Febrile convolution	1B64..
	Seizure/ Febrile convulsions	Convulsion/Febrile convolution	1B6B..
	Headache	Headache	1B1G..
Musculoskeletal	Muscle aches/ myalgia	Myalgia	N2410
	Arthropathy	Post-immunisation arthropathy	N037..

1. INTRODUCTION

The complete statistical analysis plan and results presentation is divided into 2 parts: the first part detailing the analyses to be performed (known as SAP, current document) and a second part, annex (called TFL) describing the flow and format of tables, figures and listings to be annexed to the Study Report.

This SAP describes the final analysis to be performed after the end of the observation period on all data pertaining to the above study.

2. DOCUMENT HISTORY

Date	Description	Protocol Version
11-DEC-2017	First version	Final protocol: 30 June 2017

3. STUDY DESIGN

3.1. Study design overview

- Type of design: prospective post-authorisation passive enhanced safety surveillance study in the United Kingdom (UK).
- Co-Sponsors: GSK and the University of Surrey, Guildford UK.
- Study vaccination period: intended to be from 01SEP2017 (start of the seasonal influenza vaccination) up to 30NOV2017.
- Study period: intended to be from 01SEP2017 (start of the seasonal influenza vaccination) up to 7 days after last study participant vaccinated.
- Study General Practitioner (GP) practices: 10 GP practices ordering mainly GSK's Fluarix Tetra vaccine for the 2017/18 season will be enrolled in the study before the start of the seasonal influenza immunisation season. These 10 GP practices will be selected based on their willingness to participate, their location (distributed across England (in London, a Northern city, and rural settings in the North and South)) and that the participating population spans different age strata, different levels of deprivation, different ethnic mix, different brand of computerised medical record systems, and different practice sizes. GP practices will also be included based on their ability to comply with the study protocol requirements.
- Study participants: subjects who receive influenza vaccination between 01SEP2017 and 30NOV2017 in the 10 enrolled GP practices and who have not opted-out of data sharing.
- Number of subjects: according to the sample size assumption (conservative approach), it was estimated to be able to reach a number of 50,000 subjects registered in the 10 enrolled GP practices with an estimate of 5,000 vaccinated subjects with 7 days of follow-up after vaccination.
- **Type of study:** self-contained.

3.2. Risk groups for influenza vaccination

As mentioned in the protocol, the 2017/2018 influenza plan recommends the following groups to be vaccinated in the UK:

- All children aged two to eight (but not nine years or older) on 31 August 2017 (with live attenuated influenza vaccine (LAIV))
- All primary school-aged children in former primary school pilot areas (with LAIV)
- Those aged six months to under 65 years in clinical risk groups
- Pregnant women
- Those aged 65 years and over
- Those in long-stay residential care homes
- Carers

The list above is not exhaustive, and the healthcare practitioner should apply clinical judgement to take into account the risk of influenza exacerbating any underlying disease.

3.3. Safety surveillance methods of study subjects

Two different surveillance approaches will be used to provide information about the seasonal influenza vaccine safety:

- Passive surveillance: data collected routinely and recorded in the Electronic Health Record (EHR) system by GP practices.
- Enhanced component: adverse drug reaction (ADR) cards completed by subjects vaccinated with a seasonal influenza vaccine and recorded subsequently in EHR by GP practices.

3.3.1. EHR data from passive surveillance

All 10 enrolled GP practices will be asked to record data into each subject's EHR in the usual way, using a preferred codes list (refer to [Annex 2](#)).

3.3.2. Adverse Drug Reaction card

In order to facilitate the coding of data using a standardised approach, the 10 enrolled GP practices will also distribute an ADR card to their subjects receiving seasonal influenza vaccine or, as appropriate, to their parent or carer.

Subjects will be instructed to record adverse events (refer to [Annex 3](#)) within 7 days following vaccination and to return the card to their GP practice not later than 14 days post-vaccination. Data recorded on these cards will then be recorded by the GP staff into the subject's EHR. The coding will follow a standardised approach to data recording (refer to [Annex 2](#)) and will include a specific code to indicate that the information is derived from those cards.

Of note, the intent will be to issue cards to all vaccinated patients belonging to the enrolled GP practices, however, considering the UK influenza vaccination plan, some vaccinations are expected to occur outside of the GP settings. These are described as opportunistic vaccination, performed by third parties including pharmacists and thus it cannot be excluded that for some patients, ADR cards will not be distributed. These vaccinations will still be encoded in the EHR and those subjects will be included in the study. The adverse events (AEs) will be captured through the routine data collection process (refer to Section 3.3.1).

3.4. Data extract from EHR

The following data from subjects in the 10 enrolled GP practices will be imported (anonymised) into the secure servers of the University of Surrey:

- Demographic information: age, gender, ethnicity, date of registration
- Seasonal influenza vaccine information: date of administration, brand and batch number when available
- Postcode: to understand any inequities in access according to level of social deprivation using Geographical Information System (GIS) methods. Full postcodes will be immediately transformed into deprivation scores, using the Index of Multiple Deprivation (IMD), within GP computer systems upon extraction
- Primary care consultations following vaccination, any other markers of health care utilisation, and referral to further care.
- Pre-specified European Medicines Agency (EMA) adverse events of interest (AEIs) ([Annex 2](#)) or any other reported AE recorded in the EHR. Only coded data (Read code and CTV3), i.e. where the GP codes a disease or symptom into the EHR system, will be extracted
- Data from at least one year prior to the start of the study to determine the category of UK Chief Medical Officer (CMO)-specified risk group for influenza vaccination the subjects belong to:
 - Life-style/risk factors – e.g. body mass index, smoking status
 - Records of other diseases and long term conditions – e.g. chronic respiratory disease, chronic heart disease, chronic kidney disease, chronic liver disease, chronic neurological disease, diabetes, immunosuppression, pneumonia, etc
- Pregnancy status during the course of the study period

No individual patient level data will be released to GSK.

GSK will be blind to GP practice identities, and the locality at which any AE occurs.

3.5. Summary of different groups

The following groups will be used for the statistical analyses.

Vaccine groups for vaccinated subjects:

Group name	Group order in tables	Group label in tables
Vaccine	1	Vaccinated (GSK's Fluarix Tetra)
	2	Vaccinated (Non-GSK)
	3	Vaccinated (Unknown)
	4	Vaccinated (All)

Age groups (categories recommended by EMA):

Group name	Group order in tables	Group label in tables
Age	1	6 months to 5 years
	2	6-12 years
	3	13-17 years
	4	18-65 years
	5	>65 years

UK CMO-specified risk groups*; note that subjects may be assigned in more than one specified risk group:

Group name	Group order in tables	Group label in tables
UK CMO-specified risk groups	1	Any risk group
	2	Asthma
	3	Chronic Respiratory Disease
	4	Chronic Heart Disease
	5	Chronic Kidney Disease
	6	Chronic Liver Disease
	7	Diabetes
	8	Immunosuppression (includes relevant cancer treatment)
	9	Chronic Neurological Disease
	10	Asplenia
	11	Carer
	12	Pregnancy
	13	2 to 8 years old
	14	65 years old and over
	15	Not at risk

* Some high risk groups e.g. in residential care are not well recorded in GP data

UK CMO-specified risk status:

Group name	Group order in tables	Group label in tables
UK CMO-specified risk status	1	At risk
	2	Not at risk

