Groups eligible for flu vaccination are based on the recommendation of the Joint Committee on Vaccination and Immunisation (JCVI). The national flu immunisation programme aims to provide direct protection to those who are at higher risk of flu associated morbidity and mortality. This includes older people, pregnant women, and those with certain underlying medical conditions. In 2012 JCVI recommended extending vaccination to children to provide both individual protection to the children themselves and reduce transmission across all age groups by recommending an intranasal live attenuated influenza vaccine (LAIV).

In the UK, 2017/2018 influenza plan recommended the following groups to be vaccinated^v:

- all children aged two to eight (but not nine years or older) on 31 August 2017 (with LAIV)
- All primary school-aged children in former primary school pilot areas (with LAIV)
- Those aged six months to under 65 years in clinical risk groups
- Pregnant women
- Those aged 65 years and over
- Those in long-stay residential care homes
- Carers

In 2017/18 changes to the programme are as follows:

- **Morbidly obese:** Vaccination of the morbidly obese (defined as body mass index [BMI] of 40 and above) will attract a payment under the directed enhanced services (DES) in 2017/18.
- **Age segments in children to receive the seasonal vaccination (children aged 4-5 years):** These children will now be offered flu vaccination (LAIV) in reception class, rather than through general practice. No payment will be made under the DES if they are vaccinated in general practice (unless the child is in an at risk group);
- **School Year 4 (children aged 8-9 years):** As part of the phased roll-out of the children's programme, this year children in school year 4 will also be offered the vaccination.

Eligible adults aged 18 years and over will have the choice of getting their flu vaccine at a pharmacy the Community Pharmacy Seasonal Influenza Vaccination Advanced Service. Of note, the intent will be to issue cards to all vaccinated patients belonging the recruited practices, however, considering the UK influenza vaccination plan, some vaccinations are expected to occur outside of the GP settings describe as opportunistic vaccination, perform by third parties including pharmacist and thus it cannot be excluded that for some patients, ADR cards are not distributed. The AEIs will however be captured through the routine data collection process.

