4.1. Primary objectives

- To estimate the weekly and cumulative incidence rates of AEIs within 7 days following vaccination with any seasonal influenza vaccine using card-based ADR reporting system. Data will be presented overall, by brand (Fluarix Tetra vs. others), by age strata, and UK CMO-specified risk groups status (at risk/not at risk)

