5. ENDPOINTS

5.1. Primary endpoints

- Occurrence of AEIs ([Annex 2](#)) within 7 days post vaccination reported using a card-based ADR reporting system overall, by age strata (6 months to 5 years; 6 to 12 years; 13 to 17 years; \geq 18-65 years; $>$ 65 years) and UK CMO-specified risk groups status (at risk/not at risk), each week and cumulatively, overall and by vaccine brand (Fluarix Tetra vs. others). AEIs will be presented by system organ categories

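### The single Non-GSK group in SAP 3.5 takes in intranasal LAIV given mainly to children, so the all-ages and individual-AEI brand rows mix product type and age with brand

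*SAP*

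**What the plan says.** SAP 3.5 defines four vaccine groups: Fluarix Tetra, Non-GSK, Unknown and All. The second, "Vaccinated (Non-GSK", is not divided by route or by live or inactivated type. SAP 4.1 covers events "following vaccination with any seasonal influenza vaccine using card-based ADR reporting system", so LAIV is not excluded. SAP 5.1 presents the primary endpoint "each week and cumulatively, overall and by vaccine brand (Fluarix Tetra vs. others", with age strata and risk status alongside.

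LAIV is expected among the vaccinees. SAP 3.2 lists "All children aged two to eight (but not nine years or older) on 31 August 2017" as LAIV recipients, and the protocol introduction has the same entry. That introduction describes the extension of the programme to children as "recommending an intranasal live attenuated influenza vaccine (LAIV". For ages 4 to 5 it adds: "These children will now be offered flu vaccination (LAIV) in reception class, rather than through general practice". On vaccinations given outside the practice, SAP 3.3.2 says: "These vaccinations will still be encoded in the EHR and those subjects will be included in the study". It accepts that such subjects may not receive an ADR card.

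SAP 7.3.2 gives rates by vaccine group for any AEI, each category and each individual AEI. Its tables by age group and risk status cover only any AEI, the categories and SAEs. SAP 7.3.3 repeats this for all vaccinees, with or without a card. SAP 7.2 splits Non-GSK by coded brand, but only to count vaccinated subjects.

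**The concern.** The introduction to the protocol cites the need for product-specific surveillance, and the main outputs place Fluarix Tetra beside other vaccines. If Non-GSK contains a live intranasal product given to young children, a gap between the two rows can come from route, product type or age rather than from brand. A real difference between injectable products can be hidden in the same way.

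The AEI list makes this plausible. It includes runny nose, blocked nose, nosebleed and cough. It also includes local erythema, which the code list in Protocol Appendix 7 describes as occurring at the injection site. The individual symptoms are the rows with no age breakdown. The enrolled practices order mainly Fluarix Tetra, so Non-GSK is largely what falls outside that order, and childhood LAIV is an expected part of it.

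**Working it through.** **The plan's own figure.** No precision or power is stated for the brand rows. Table 1 gives precision for all vaccinees together. For n = 5,000 and p = 1%:

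- relative standard error = sqrt((1-p)/(np)) = sqrt(0.99/50) = 14.1%
- Clopper-Pearson 95% CI for 50/5,000 = 0.74% to 1.32% (printed as 0.7% to 1.3%)
- P(at least one event) = 1-(1-p)^n > 99.99%

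All three agree with the table. They do not bear on the mixing.

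**Where the mixing reaches.**

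| Output | Split by brand | Split by age | LAIV mixed in? |
|---|---|---|---|
| All-ages rates, SAP 7.3.2 and 7.3.3 | yes | no | yes |
| Individual AEIs, SAP 7.3.2, 7.3.3 and 7.3.6 | yes | no | yes |
| Weekly report AEI rates, SAP 9.1.1 | yes | none stated | yes |
| RCGP RSC rates, SAP 7.3.7 | yes | no | yes |
| Any AEI, categories, SAEs: 6 months-5 years and 6-12 years | yes | yes | yes, since ages 2 to 8 straddle both strata |
| Any AEI, categories, SAEs: 13 years and over | yes | yes | little or none under the stated plan |

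**Size, under assumptions.** Let s be the LAIV share of Non-GSK, r the AEI rate in LAIV recipients relative to injectable recipients (age and route together), and p the injectable rate, equal for both brands. The documents give none of these. Fluarix Tetra is taken to be injectable, which they do not state outright.

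Non-GSK rate = (1-s)p + s·r·p, so the Non-GSK/Fluarix Tetra ratio = 1 + s(r-1).

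| r | s = 20% | s = 50% | s = 80% |
|---|---|---|---|
| 0 | 0.80 | 0.50 | 0.20 |
| 0.5 | 0.90 | 0.75 | 0.60 |
| 2 | 1.20 | 1.50 | 1.80 |
| 3 | 1.40 | 2.00 | 2.60 |

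The row r = 0 is the limiting case of a reaction that only an injection can cause. Removing LAIV from Non-GSK returns the ratio to 1.00 in every cell.

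**Would it show against the confidence intervals?** Take the 5,000 expected vaccinees (SAP 3.1) and assume 80% received Fluarix Tetra (4,000 against 1,000), with s = 50%, r = 2 and no brand effect:

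- p = 5%: 5.00% (4.35 to 5.72) against 7.50% (5.94 to 9.31). The intervals separate.
- p = 1%: 1.00% (0.72 to 1.36) against 1.50% (0.84 to 2.46). They overlap.
- p = 5% with 90% on Fluarix Tetra: 5.00% (4.38 to 5.68) against 7.50% (5.35 to 10.17). They overlap.

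These are exact intervals without clustering. A design effect above 1 would widen them.

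**The case against.** The strongest reply is that the plan makes no formal brand comparison. SAP 3.1 calls the study self-contained, SAP 8 says all analyses are descriptive, and SAP 9.2 rules out hypothesis testing. No brand ratio or difference is computed. The protocol synopsis says findings will be discussed against the RCGP network, GSK clinical trials and the two earlier pilots. This stands, and it limits the consequence. It does not remove the mixing from rows that readers will set side by side.

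A reader might infer that every brand result is confounded and that age stratification does nothing. The documents do not support that. SAP 7.3.2 gives respiratory and local-symptom categories by age group, and from age 13 up these should hold little or no LAIV.

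A reader might also infer that all LAIV sits in Non-GSK and affects both objectives equally. SAP 3.4 extracts brand only when available, and SAP 3.5 has an Unknown group for the rest. LAIV given at school may come without a card, and the primary denominator requires one.

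Nor do the documents show a direction. They give no LAIV event rates, so it cannot be said that pooling flatters Fluarix Tetra. Even r = 0 for local reactions is only a limit, because the card item asks about a local reaction to the vaccine and is not confined to injection.

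Finally, the table templates are in a separate document that was not available, so a further split or footnote there cannot be excluded.

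**Conclusion.** The point holds with a limited scope. The all-ages brand rows, all individual-AEI rates, the weekly report rates and the RCGP RSC rates mix product type and age with brand, and route stays mixed in the two youngest strata. The category tables from age 13 up are largely free of this, and the card-based primary analysis is probably affected less than the secondary analysis of all EHR data.

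The size cannot be fixed from the documents. Over LAIV shares of 20% to 80%, the spurious ratio runs from 0.90 to 0.60 at r = 0.5 and from 1.20 to 1.80 at r = 2. Whether that would be visible depends on the base rate and the brand split. The conclusion assumes that Fluarix Tetra is injectable, that LAIV is recorded as a brand other than GSK's, and that practices follow the stated programme. It is a cheap improvement to how descriptive results are read, not a fault that invalidates them.

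**What to change.** Using the recorded brand, add a Non-GSK injectable group (Non-GSK excluding LAIV) to SAP 3.5. Show it beside Fluarix Tetra in the cumulative Weeks 35-48 tables, including individual AEIs and local symptoms, overall and by age group. The age breakdown is needed because removing LAIV alone does not balance age in the overall rows. The RCGP RSC table is also cumulative and can carry the same group. Leave the weekly tables undivided, with a footnote that Non-GSK includes LAIV, because splitting 14 weekly cohorts would give sparse cells.

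Show LAIV as its own column only if that is compatible with the aim in SAP 7.2 of not disclosing other manufacturers' information.

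The cost is one extra group in the cumulative tables and smaller counts in the Non-GSK rows. If LAIV is shown, another manufacturer's product might be disclosed indirectly. No new data are needed, since brand is already extracted when available.

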- To understand any inequities in access according to level of social deprivation using Geographical Information System (GIS) methods, full postcodes will be immediately transformed into deprivation scores, using the Index of Multiple Deprivation, within GP computer systems upon date extraction.
- Primary care consultations following vaccination, any other markers of health care utilisation, and referral to further care.
- AEIs (Appendix 2) or any other reported AE recorded in the EHR.
- Data from at least one year prior to the start of the study to determine the category of UK CMO-specified risk group for influenza vaccination the subjects belong to:
 - Life-style/risk factors, CMO risk status – e.g. BMI, smoking status.
 - Records of other diseases and long term conditions – e.g. chronic respiratory disease, chronic heart disease, chronic kidney disease, chronic liver disease, chronic neurological disease, diabetes, immunosuppression, pneumonia, etc.
 - Pregnancy status during the course of the study period.

Sample size consideration

The average practice size in England is 7,034 patients^{xvi}, an estimate of approximately 70,340 patients are expected to be registered (across the ten participating GP practices). Of note, in the period from September to December 2016, the seasonal influenza vaccine uptake for over 65 year olds was 71.0%; for those in a clinical risk group aged 6 months to 65 years old, the uptake was 45.1%; and for pregnant women, it was 42.3%. The estimate of influenza vaccine uptake had been made estimated using the coverage estimates published by Public Health England (PHE)^{xvii}.

The eligible target population to be medically followed by the GPs would be estimated at 50,000 subjects (approximately 5,000 per practice using a conservative approach). As per EMA Pharmacovigilance Risk Assessment Committee (PRAC)/Vaccine Working Party (VWP) request, at least 1,000 vaccinated subjects with 7 days of follow-up after vaccination are targeted to be enrolled. In this study, up to 5,000 vaccinated subjects with 7 days of follow-up after vaccination are expected to be enrolled. This sample size estimation sets out to estimate the probability to observe at least

one AEI in the study population and evaluate the level of "certainty" around this finding; over a 14 week-surveillance period (01 September – 30 November 2017).

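### SAP 3.5 has no morbid-obesity risk group, so vaccinees who qualify only by BMI would be reported as not at risk

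*SAP*

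**What the plan says.** SAP 3.5 sets out 15 ordered rows for the CMO-specified risk groups. The first is "Any risk group" and the last is *Not at risk*. Between them stand nine clinical conditions (asthma to asplenia), carer, pregnancy, "2 to 8 years old" and "65 years old and over". A two-level status, *At risk* / *Not at risk*, follows. A footnote says that some high-risk groups, with residential care as the example, are poorly recorded in GP data.

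In Protocol section 4, under the 2017/18 changes to the programme: "Vaccination of the morbidly obese (defined as body mass index [BMI] of 40 and above) will attract a payment".

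Protocol section 5 (data extraction) lists, among the data used to determine the CMO risk group: "Life-style/risk factors, CMO risk status – e.g. BMI, smoking status". SAP 3.4 repeats that purpose and names "body mass index, smoking status".

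SAP 7.3.2 reports card-based AEI rates by age group and by the two-level risk status. SAP 7.3.3 repeats those analyses with all AEIs entered in the EHR.

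**The concern.** Risk status is one of the presentations named in the primary objective, so its derivation should match the programme that the protocol describes. BMI is collected to assign risk status, but nothing in the SAP's list uses it. A programmer following SAP 3.5 literally would place a vaccinee whose only qualifying feature is a BMI of 40 or above in *Not at risk*. That group's AEI rates would then include people whom the protocol treats as part of the targeted programme. The uptake table by risk group in SAP 7.2 would also have no row for them.

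**Working it through.** The plan states no figure on this point to reproduce. The check compares the texts.

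**1. Does any SAP group use BMI?** Rows 2 to 10 are clinical conditions, 11 is carer, 12 is pregnancy, and 13 and 14 are age groups. None uses BMI.

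**2. How is *At risk* formed?** The SAP does not say in words. Because the list opens with "Any risk group" and closes with *Not at risk*, the natural rule is that *At risk* means membership of at least one of rows 2 to 14. The rest of this check depends on that inference.

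**3. Who is affected?** Only vaccinees who meet all of these:
- BMI of 40 or above;
- not aged 2 to 8 and not aged 65 or over;
- none of the listed conditions, not pregnant and not a carer.

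Morbidly obese subjects with any other criterion are already at risk.

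**4. Where does it show?** In the weekly and cumulative rates by risk status for any AEI, each AEI category and SAEs, from cards (SAP 7.3.2) and from all EHR data (SAP 7.3.3). Let *b* be the number who qualify only by BMI, *N* the other *Not at risk* vaccinees, and p1 and p0 their AEI proportions. The reported *Not at risk* proportion is (N·p0 + b·p1)/(N + b), which differs from p0 by [b/(N + b)]·(p1 − p0). The documents give none of *b*, *N*, p1 or p0 for these groups, so neither the size nor the direction of the shift can be computed.

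**5. Is the omission explained?** The SAP 3.5 footnote does not mention obesity. SAP section 10 records only that cohorts and incidence rates were clarified. SAP 3.2 calls its list of groups non-exhaustive, but in the context of a practitioner's judgement; that gives no rule for a derived variable.

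**6. What do the two age rows do?** Taking the SAP 3.5 labels at face value:

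| Age stratum | At risk by age alone |
|---|---|
| 6 months to 5 years | ages 2 to 5 |
| 6 to 12 years | ages 6 to 8 |
| 13 to 17 years | none |
| 18 to 65 years | age 65 only |
| over 65 years | all (100%) |

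*Not at risk* can therefore contain only ages 6 to 23 months and 9 to 64.

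**The case against.** The strongest reply on obesity is that the protocol's bulleted list of groups recommended for vaccination does not include the morbidly obese. They appear separately, as a group whose vaccination attracts a payment. Extracting BMI does not prove that a group was intended, since smoking status and pneumonia are extracted under the same heading and have no row either. These points make this a gap between the documents rather than a direct contradiction. They do not remove it: the protocol gives the BMI threshold, places BMI under CMO risk status, and the SAP neither uses it nor says why not.

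On age, a reader might infer that it is an error to class everyone aged 65 or over, or 2 to 8, as at risk. The documents do not support that. The Protocol section 4 list includes both groups, and SAP 3.2, headed as risk groups, does too, including "Those aged 65 years and over". No objective compares people with clinical conditions against others, and all analyses are descriptive. SAP 7.3.2 does not say that age and risk status are crossed, so an empty *Not at risk* cell over 65 is not a planned table cell.

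A reader might also infer that the split mostly repeats age. An illustration uses the uptakes in the protocol's sample size section (71.0% over 65, 45.1% clinical risk, 42.3% pregnant) with assumed population shares and an assumed uptake at ages 2 to 8. The share of *At risk* vaccinees who fall in an age row then runs from 0.12×0.71 / (0.12×0.71 + 0.16×0.451 + 0.03×0.423) = 0.0852/0.1701 = 50% to (0.20×0.71 + 0.09×0.40) / (0.20×0.71 + 0.09×0.40 + 0.08×0.451 + 0.01×0.423) = 0.178/0.2183 = 82%. The shares are not in the documents, and at ages 9 to 64 the split still reflects condition, pregnancy or carer status.

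**Conclusion.** The point holds for obesity only. As written, SAP 3.5 places vaccinees who qualify only by BMI in *Not at risk*, in a presentation named in the primary objective. This rests on reading *At risk* as membership of any listed group.

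The size is unknown and probably small. One could assume 25 to 200 such subjects beside 400 others in *Not at risk* and obtain 25/425 = 6% to 200/600 = 33% of that group. Those counts have no source in the documents, so the range shows arithmetic and not the extent of the problem. No effect on any AEI rate has been shown.

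The age rows follow the programme definition. Their consequence is a limit on interpretation: the pooled *At risk* versus *Not at risk* comparison is confounded with age and should not be read as the effect of clinical conditions.

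**What to change.** 1. Add a row for morbid obesity (BMI of 40 and above) to the SAP 3.5 risk groups and count it in *Any risk group* and *At risk*.
2. State in one sentence how *At risk* is derived from the listed groups.
3. Report how many vaccinees have no recorded BMI.

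The cost is one derived flag, one row and one count, from data already extracted. Because the analyses are descriptive, no type I error is spent. The downside is that BMI may be incomplete in GP records, so some morbidly obese subjects would still be counted as *Not at risk*; item 3 shows how far that could go.

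Optional: a descriptive table of clinical-condition risk (rows 2 to 10 plus morbid obesity, yes/no) within age strata, beside the programme-based split. With about 5,000 vaccinees expected over five strata, some cells are likely to be sparse.
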